#### 11.1.3.1 Evaluation of Target Lesions

Complete Response (CR): Disappearance of all target lesions. Any pathological lymph nodes (whether target or non-target) must have reduction in short axis to <10 mm.

Partial Response (PR): At least a 30% decrease in the sum of the diameters of target lesions, taking as reference the baseline sum diameters.

Progressive Disease (PD): At least a 20% increase in the sum of the diameters of target lesions, taking as reference the smallest sum on study (this includes the baseline sum if that is the smallest on study). In addition to the relative increase of 20%, the sum must also demonstrate an absolute increase of at least 5 mm. (Note: the appearance of one or more new lesions is also considered progressions).

Stable Disease (SD): Neither sufficient shrinkage to qualify for PR nor sufficient increase to qualify for PD, taking as reference the smallest sum diameters while on study.

#### 11.1.3.2 Evaluation of Non-Target Lesions

Complete Response (CR): Disappearance of all non-target lesions and normalization of tumor marker level. All lymph nodes must be non-pathological in size (<10 mm short axis).

Note: If tumor markers are initially above the upper normal limit, they must normalize for a patient to be considered in complete clinical response.

Non-CR/Non-PD: Persistence of one or more non-target lesion(s) and/or maintenance

of tumor marker level above the normal limits.

**Progressive Disease (PD):** Appearance of one or more new lesions and/or *unequivocal progression* of existing non-target lesions. *Unequivocal progression* should not normally trump target lesion status. It must be representative of overall disease status change, not a single lesion increase.

Although a clear progression of “non-target” lesions only is exceptional, the opinion of the treating physician should prevail in such circumstances, and the progression status should be confirmed at a later time by the review panel (or Principal Investigator).

### 11.1.3.3 Evaluation of New Lesions

The finding of a new lesion should be unequivocal (i.e. not due to difference in scanning technique, imaging modality, or findings thought to represent something other than tumor (for example, some ‘new’ bone lesions may be simply healing or flare of pre-existing lesions). However, a lesion identified on a follow-up scan in an anatomical location that was not scanned at baseline is considered new and will indicate PD. If a new lesion is equivocal (because of small size etc.), follow-up evaluation will clarify if it truly represents new disease and if PD is confirmed, progression should be declared using the date of the initial scan on which the lesion was discovered.

### 11.1.3.4 Evaluation of Best Overall Response

The best overall response is the best response recorded from the start of the treatment until disease progression/recurrence (taking as reference for progressive disease the smallest measurements recorded since the treatment started). The patient's best response assignment will depend on the achievement of both measurement and confirmation criteria.

#### For Participants with Measurable Disease (i.e., Target Disease)

Target Lesions	Non-Target Lesions	New Lesions	Overall Response	Best Overall Response when Confirmation is Required*
CR	CR	No	CR	4 wks Confirmation**
CR	Non-CR/Non-PD	No	PR	4 wks Confirmation**
CR	Not evaluated	No	PR	
PR	Non-CR/Non-PD/not evaluated	No	PR	
SD	Non-CR/Non-PD/not evaluated	No	SD	
PD	Any	Yes or No	PD	no prior SD, PR or CR
Any	PD***	Yes or No	PD	
Any	Any	Yes	PD	

\* See RECIST 1.1 manuscript for further details on what is evidence of a new lesion.  
 \*\* Only for non-randomized trials with response as primary endpoint.  
 \*\*\* In exceptional circumstances, unequivocal progression in non-target lesions may be accepted as disease progression.

Note: Participants with a global deterioration of health status requiring discontinuation of treatment without objective evidence of disease progression at that time should be reported as “*symptomatic deterioration.*” Every effort should be made to document the objective progression even after discontinuation of treatment.

**For Participants with Non-Measurable Disease (i.e., Non-Target Disease)**

Non-Target Lesions	New Lesions	Overall Response
CR	No	CR
Non-CR/non-PD	No	Non-CR/non-PD*
Not all evaluated	No	not evaluated
Unequivocal PD	Yes or No	PD
Any	Yes	PD
* ‘Non-CR/non-PD’ is preferred over ‘stable disease’ for non-target disease since SD is increasingly used as an endpoint for assessment of efficacy in some trials so to assign this category when no lesions can be measured is not advised		

11.1.4 Duration of Response

Duration of overall response: The duration of overall response is measured from the time measurement criteria are met for CR or PR (whichever is first recorded) until the first date that recurrent or progressive disease is objectively documented (taking as reference for progressive disease the smallest measurements recorded since the treatment started, or death due to any cause. Participants without events reported are censored at the last disease evaluation).

Duration of overall complete response: The duration of overall CR is measured from the time measurement criteria are first met for CR until the first date that progressive disease is objectively documented, or death due to any cause. Participants without events reported are censored at the last disease evaluation.

Duration of stable disease: Stable disease is measured from the start of the treatment until the criteria for progression are met, taking as reference the smallest measurements recorded since the treatment started, including the baseline measurements.

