- j. Tumor assessments should consist of 1) CT and/or MRI of the chest/abdomen/pelvis, 3) any other imaging studies (CT neck, plain films, etc.) as clinically indicated by the treating physician. The same radiographic procedures and technique must be used throughout the study for each patient (e.g., if the patient had CT chest/abdomen/pelvis performed during screening, then she should subsequently undergo CT performed using the same radiologic protocol throughout the remainder of the study). Tumor assessments will be performed at baseline, at day 1 ( $\pm 7$  day scheduling window) of Cycles 2, 3, and 4 and then every 12 week [ at day 1 ( $\pm 7$  day scheduling window) of every odd cycle: C6, C8, C10, etc.]. Additional scans are permitted as clinically indicated. All known sites of disease documented at screening should be re-assessed at each subsequent tumor evaluation.
- k. For those taken off the study for reasons other than progressive disease, tumor measurements should continue to be repeated every 6-12 weeks until first disease progression or start of a new anti-cancer therapy. Every effort should be made to maintain this scheduled, but it is understood that it may not be possible in all cases. Failure to complete scans at this interval will not be deemed protocol violations.
- l. Collected at screening, every restaging, end of treatment (if removed for progressive disease) and optionally at time of progression. See section 9.0
- m. Baseline tumor biopsy should be obtained within 28 days prior to initiating protocol therapy. On treatment biopsies should be obtained at C1D29 (+14 day scheduling window). A tumor biopsy may be performed at the end of treatment. See Section 9.2.
- n. Archival tumor sample should be collected (block or if not possible, 10-20 5micron, unstained positively charged slides). This sample may be collected at any time throughout the lifetime of the study.
- o. Baseline stool collection should be obtained within 14 days before starting protocol therapy. On treatment stool collection should be obtained at C1D29 (anytime from C1D29-C2D1). A stool collection should be obtained at the end of treatment. As these collections are for exploratory correlative purposes, failure to provide a sample at these timepoints will not constitute a protocol violation. See section 9 and/or lab manual for stool collection and processing instructions.

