## 11. MEASUREMENT OF EFFECT

For the purposes of this study, participants should be re-evaluated for response approximately every 6 weeks for the first 24 weeks and then every 12 weeks thereafter. If cycles are delayed for any reason, the scan schedule should be moved to align with cycles of treatment received.

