11.1.5 Clinical Benefit rate

Clinical benefit rate: defined as CR, PR and stable disease (SD)  $\geq$  24 weeks.

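### The clinical benefit rate has no week-24 landmark, so progression first found on or after day 168 still counts as stable disease of at least 24 weeks

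*Combined protocol and SAP*

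**What the plan says.** Clinical benefit is a secondary endpoint by RECIST 1.1 and by irRC (Sections 1.3.3, 1.3.5 and 13.1). Section 11.1.5 reads "Clinical benefit rate: defined as CR, PR and stable disease (SD", followed by the threshold of 24 weeks or more. Section 13.4 repeats this and reports CBR with a 95% exact confidence interval.

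Section 11.1.4 fixes the length of stable disease: "Stable disease is measured from the start of the treatment until the criteria for progression are met". The two response-duration definitions above it in the same section also end at death and censor at the last evaluation. The SD definition has neither clause. In the best-response table of Section 11.1.3.4, progression is the best response only where there is "no prior SD, PR or CR", so a patient with stable scans followed by progression keeps SD as best response.

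The scan schedule is stated in two ways:

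- Section 11 re-evaluates patients "approximately every 6 weeks for the first 24 weeks and then every 12 weeks thereafter", which implies scans at weeks 6, 12, 18 and 24.
- Study Calendar footnote j puts scans, with a ±7-day window, at day 1 of cycles 2, 3 and 4 and 12-weekly after that. It labels the later scans odd cycles but lists C6, C8 and C10. Section 9.3 names the same restaging visits for blood collection: C2D1, C3D1, C4D1, C6D1 and C8D1.

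**The concern.** The 24-week threshold is the same day as a scheduled scan on the Section 11 schedule, and SD is timed to the scan that finds progression. The scan that shows the patient has progressed can therefore also complete the 24 weeks of stability. Two patients with the same tumor course, both last shown stable at week 18, can be classified differently because of an appointment date.

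CBR would then include some patients who had progressed by the landmark that defines benefit, and the number would depend on scan timing and on which of the two schedules is followed. If the reading is chosen only when CBR is analyzed, that choice can be influenced by the data.

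**Working it through.** The plan gives no CBR target, rate or power, so there is no stated figure to reproduce. The check applies the written definitions and then sizes the effect.

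**Dates.** Cycles last 42 days (Section 5.1, Table 1), so day 1 of cycle k falls 6(k − 1) weeks after the first dose. C4D1 is week 18 (day 126), C5D1 is week 24 (day 168) and C6D1 is week 30 (day 210).

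**Individual records, Section 11 schedule.** Take SD at weeks 6, 12 and 18, then progression at the week-24 scan.

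- Scan on day 170: 170/7 = 24.3 weeks, counted as benefit.
- Scan on day 168: 24.0 weeks, counted.
- Scan on day 166: 166/7 = 23.7 weeks, not counted.
- Of the 15 whole days in the window (161 to 175), 8 give at least 168 days and 7 do not.

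**Individual records, listed visits.** With SD at week 18 and progression at week 30, SD lasts 30 weeks and is counted, although nothing was observed between weeks 18 and 30.

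**Assumptions for size.** Time to progression in non-responders is exponential, S(d) = 0.5^(d / (median × 30.44)). Scan days are uniform over ±7 days. The documents give no median for this population, so 2 to 7.2 months is an assumed range.

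- Section 11 schedule: half the scans fall on days 168 to 175 (mean 171.5). Excess over no progression at the week-24 scan ≈ ½ × [S(126) − S(171.5)].
- Listed visits: everyone stable at week 18 is counted. Excess over the true week-24 share ≈ S(126) − S(168).

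| Median (months) | S(126) | S(168) | S(171.5) | S(210) | Excess per 100, Section 11 | Excess per 100, listed visits |
|---|---|---|---|---|---|---|
| 2 | 0.238 | 0.148 | 0.142 | 0.092 | 4.8 | 9.1 |
| 3 | 0.384 | 0.279 | 0.272 | 0.203 | 5.6 | 10.5 |
| 4 | 0.488 | 0.384 | 0.377 | 0.303 | 5.6 | 10.4 |
| 5.5 | 0.594 | 0.499 | 0.492 | 0.419 | 5.1 | 9.5 |
| 7.2 | 0.671 | 0.588 | 0.581 | 0.515 | 4.5 | 8.4 |

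The last two columns were computed before rounding. A simulation with continuous windows gives the same Section 11 figures.

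**In patients.** At the design response rate of 25%, 30 × 0.75 = 22.5 are non-responders. Section 11 schedule: 22.5 × 0.045 = 1.0 to 22.5 × 0.056 = 1.3. Listed visits: 22.5 × 0.084 = 1.9 to 22.5 × 0.105 = 2.4.

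**Alternative rules, same assumptions.**

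- Requiring no progression at the week-24 scan is essentially unbiased for S(168) on the Section 11 schedule.
- Timing SD to the last clean scan gives about ½S(171.5) + ½S(252). At a median of 3 months this is ½(0.272) + ½(0.148) = 0.210, against a true 0.279. Over the range of medians it undercounts by about 5 to 8 points.
- If there is no week-24 scan, requiring a clean week-30 scan undercounts by S(168) − S(210), about 6 to 8 points.

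**The case against.** Dating to documented progression is the plan's consistent convention: response duration (Section 11.1.4) and PFS (Section 13.4) end the same way. Under a landmark rule a patient could have PFS of 24.3 weeks and yet no clinical benefit. CBR is also descriptive, with no test or decision attached; at 15 of 30 its exact 95% interval runs from 31% to 69%, so one patient is small beside the sampling error. All of this stands. It limits the importance of the point but does not supply the missing landmark.

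Several stronger readings are tempting, and the documents do not support them:

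- *Every patient progressing at the week-24 scan is counted.* Scans on days 161 to 167 give less than 24 weeks and are not counted.
- *SD should be timed to the last clean scan.* That undercounts by about as much as the present rule overcounts, or more.
- *The present rule can only add patients.* Footnote j permits extra scans. A clean scan on day 161 followed by progression on an unscheduled scan on day 165 fails the present rule (165/7 = 23.6 weeks) but would pass a landmark with a −7-day allowance.
- *Without a death or censoring clause, SD never ends.* No section says SD continues after death or loss to follow-up. This is a drafting gap.
- *The problem is independent of the scan schedule.* The listed visits contain no week-24 scan, so both its size and its repair depend on the schedule.
- *One wording serves irRC too.* Section 11.1.4 sits under RECIST. Section 11.3.1.4 recommends confirming irPD in difficult cases, and Section 11.3.1.5 uses all available assessments for best response. The RECIST wording could disqualify an unconfirmed irPD that later reverses.

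**Conclusion.** The point holds in a limited form. Progression found at a scan on or after day 168 literally counts as SD of at least 24 weeks, even when the last progression-free scan was at week 18, and no other section overrides this.

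On the Section 11 schedule the excess is about 4.5 to 5.6 per 100 non-responders, or 1.0 to 1.3 patients at the design response rate (about 3 to 4 points of CBR in 30 patients). On the visits listed in footnote j and Section 9.3 it is about 8 to 11 per 100, or 1.9 to 2.4 patients. These figures rest on assumed exponential medians of 2 to 7.2 months and uniform scan windows. The classification rule itself rests only on the text.

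A reader might infer that the trial's conclusion is at risk. It is not: the primary ORR and the two-stage rule do not use SD duration. This is an inexpensive correction to a secondary endpoint, worth making before CBR is analyzed.

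**What to change.** 1. Reconcile Section 11 with Study Calendar footnote j and Section 9.3 on whether there is a week-24 scan, and correct the odd-cycle label in footnote j. This comes first because the definition depends on it.

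2. In Sections 11.1.4, 11.1.5 and 13.4, define the RECIST 1.1 criterion along these lines: *SD of at least 24 weeks requires a tumor assessment at the week-24 visit (−7 days) or later, with no progression at that or any earlier assessment. Patients who progress at that assessment, die or start other anti-cancer therapy before it, or have no such assessment, do not have SD of at least 24 weeks. All treated patients remain in the denominator.* State openly that a clean scan on day 161 (23.0 weeks) is accepted.

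3. If the schedule keeps no week-24 scan, say that the criterion is assessed at week 30 and is conservative for a 24-week rate.

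4. For irRC, write a parallel rule based on irPD that respects its confirmation provisions.

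The definition costs a few sentences and needs no new data. Step 1 adds a scan only if the sponsor chooses a schedule that has one where none is now performed. The downsides are a slightly lower reported CBR and an occasional patient with PFS just over 24 weeks who is not counted as having clinical benefit.

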11.1.5 Clinical Benefit rate

Clinical benefit rate: defined as CR, PR and stable disease (SD)  $\geq$  24 weeks.

## 11.2 Antitumor Effect – Hematologic Tumors

N/A

## 11.3 Other Response Parameters

### 11.3.1 Definition of Tumor Response Using Immune-Related Response Criteria (irRC)

The sum of the products of the largest perpendicular diameters (SPD) at tumor assessment using the immune-related response criteria (irRC) for progressive disease incorporate the contribution of new measurable lesions. Each net Percentage Change in Tumor Burden per assessment using irRC criteria accounts for the size and growth kinetics of both old and new lesions as they appear.

#### 11.3.1.1 Impact of New Lesions on irRC

New lesions in and of themselves do not qualify as progressive disease. However, their contribution to total tumor burden is included in the SPD which in turn feeds into the irRC criteria for tumor response. Therefore, new non-measurable lesions will not discontinue any subject from the study.

#### 11.3.1.2 Definition of Target Lesions Response Using irRC

- **irComplete Response (irCR):** Complete disappearance of all target lesions. This category encompasses exactly the same subjects as “CR” by the mWHO criteria.
- **irPartial Response (irPR):** Decrease, relative to baseline, or 50% or greater in the sum of the products of the two largest perpendicular diameters of all target and all new measurable target lesions (i.e., Percentage Change in Tumor Burden). Note: the appearance of new measurable lesions is factored into the overall tumor burden, but does not automatically qualify as progressive disease until the SBD increases by  $\geq 25\%$  when compared to SPD at nadir.
- **irStable Disease (irSD):** Does not meet criteria for irRC or irPR, in the absence of progressive disease.
- **irProgressive Disease (irPD):** At least 25% increase Percentage Change in Tumor Burden (i.e. taking SPD of all target lesions and any new lesions) when compared to SPD at nadir.

#### 11.3.1.3 Definition of Non-Target Lesions Response Using irRC

- **irComplete Response (irCR):** Complete disappearance of all non-target lesions. This category encompasses exactly the same subjects as “CR” by the mWHO criteria.
- **irPartial Response (irPR) or irStable Disease (irSD):** Non-target lesion(s) are not considered in the definition of PR; these terms do not apply.
- **irProgressive Disease (irPD):** Increases in number or size of non-target lesion(s) does not constitute progressive disease unless/until the Percentage Change in Tumor Burden increases by 25% (i.e. the SPD at nadir of the target lesions increases by the required amount).

#### 11.3.1.4 Definition of Overall Response Using irRC

Overall response using irRC will be based on these criteria:

- **Immune-Related Complete Response (irCR):** Complete disappearance of all tumor lesions (target and non-target) together with no new measurable/unmeasurable lesions for at least 4 weeks from the date of documentation of complete response.
- **Immune-Related Partial Response (irPR):** The sum of the products of the two largest perpendicular diameters of all target lesions is measured and captured as the SPD baseline. At each subsequent tumor assessment, the SPD of the two largest perpendicular diameters of all target lesions and of new measurable lesions are added together to provide the Immune Response Sum of Product Diameters (irSPD). A decrease, relative to baseline, of the irSPD compared to the previously SPD baseline of 50% or greater is considered an irPR.
- **Immune-Related Stable Disease (irSD):** irSD is defined as the failure to meet criteria for immune complete response or immune partial response, in the absence of progressive disease
- **Immune-Related Progressive Disease (irPD):** It is recommended in difficult cases to confirm PD by serial imaging. Any of the following will constitute PD:
  - At least 25% increase in the SPD of all target lesions over baseline SPD calculated for the target lesions.
  - At least 25% increase in the SPD of all target lesions and new measurable lesions (irSPD) over the baseline SPD calculated for the target lesions.

Criteria for determining overall response by irRC are summarized as follows:

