#### Immune-Related Response Criteria Definitions

Target Lesion Definition	Non-Target Lesion Definition	New Measurable Lesions	New Unmeasurable Lesions	Percent change in tumor burden (including measurable new lesions when present)	Overall irRC Response
Complete Response	Complete Response	No	No	-100%	irCR
Partial Response	Any	Any	Any	≥ -50%	irPR
				<-50% to <+25%	irSD
				>+25%	irPD
Stable Disease	Any	Any	Any	<-50% to <+25%	irSD
				>+25%	irPD
Progressive Disease	Any	Any	Any	≥+25%	irPD

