#### 11.3.1.5 Immune-Related Best Overall Response Using irRC (irBOR)

irBOR is the best confirmed overall response over the study as a whole, recorded between the date of first dose until the last tumor assessment before subsequent therapy (except for local palliative radiotherapy for painful bone lesions) for the individual subject in the study. For the assessment of irBOR, all available assessments per subject are considered.

irCR or irPR determinations included in the irBOR assessment must be confirmed by a second (confirmatory) evaluation meeting the criteria for response and performed no less than 4 weeks after the criteria for response are first met.

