### **13.4 Analysis of Secondary Endpoints**

#### Efficacy Endpoints

All patients who initiated protocol therapy will also be evaluated for ORR according to irRC, and for CBR and PFS, according to RECIST. Clinical benefit is defined as CR, PR or SD  $\geq$  24 weeks according to RECIST 1.1. ORR according to irRC will be reported with 90% exact confidence intervals. CBR will be reported respectively with 95% exact confidence intervals. PFS will be analyzed using Kaplan–Meier product-limit estimates and will be plotted using Kaplan-Meier plots. PFS is defined as the time from study randomization to disease progression according to RECIST 1.1, medical judgment or death due to any cause, whichever occurred first. Patients alive without disease progression are censored at the date of last disease evaluation. The hazard ratio for each time-to-event endpoint will be estimated with 95% confidence intervals derived from the Cox proportional hazard model, but no hypothesis testing will be conducted.

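### Immune-related progression is counted from nadir in 11.3.1.2 and 11.3.1.3 but from baseline in 11.3.1.4, so irRC PFS dates can differ for some patients who shrink and then regrow

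*Combined protocol and SAP*

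**What the plan says.** Section 11.3.1.2 defines target-lesion irPD as at least a 25% increase, "i.e. taking SPD of all target lesions and any new lesions) when compared to SPD at nadir". The note under irPR in the same section also uses nadir. Section 11.3.1.3 says that non-target growth does not count as progression until the tumor burden has risen by 25%, which it explains as the point where "the SPD at nadir of the target lesions increases by the required amount".

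Section 11.3.1.4 opens with "Overall response using irRC will be based on these criteria" and gives two irPD criteria. The first is "At least 25% increase in the SPD of all target lesions over baseline SPD calculated for the target lesions". The second adds new measurable lesions to the current sum and again compares it with baseline.

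The summary table that follows takes target-lesion status as an input. It puts the -50% and +25% cuts in one column headed "Percent change in tumor burden (including measurable new lesions when present"), which does not say what the change is measured from.

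Objectives 1.3.5 and 1.3.6 and Section 13.1 list clinical benefit and PFS by irRC as secondary endpoints. Section 13.4 says patients will "also be evaluated for ORR according to irRC, and for CBR and PFS, according to RECIST", and it defines the PFS event by RECIST 1.1, medical judgment or death. Section 5.5 lets patients stay on therapy past RECIST progression until irRC progression.

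**The concern.** The nadir and baseline rules are different rules for anyone whose tumor burden falls below baseline. Once it has fallen, the nadir rule is met sooner. The two can give different irPD dates from the same measurements whenever SPD regrows to at least 1.25 times nadir and is still below 1.25 times baseline at one or more scans.

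Three things depend on the choice:

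- **PFS by irRC (1.3.6).** The event date can take two values.
- **Clinical benefit by irRC (1.3.5).** This can change only for patients without a confirmed irCR or irPR who reach nadir +25% before 24 weeks.
- **Treatment beyond RECIST progression (5.5).** Two sites could read Section 11.3 differently and end the allowance at different times for the same patient.

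The ORR by irRC is largely unaffected. Partial response is judged from baseline in both sections, and Section 11.3.1.5 states that "irBOR is the best confirmed overall response over the study as a whole". No RECIST 1.1 endpoint is involved, including the primary.

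**Working it through.** The plan gives no figure here to reproduce, so the check compares the two rules directly.

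**Inputs**

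- Nadir rule: 11.3.1.2 and 11.3.1.3. Baseline rule: 11.3.1.4.
- irPR: a fall of at least 50% from baseline (11.3.1.2, 11.3.1.4), confirmed no less than 4 weeks later (11.3.1.5).
- Clinical benefit: response, or stable disease for at least 24 weeks (1.3.5).
- Scan weeks: Study Calendar, footnote j, gives day 1 of cycles 2, 3 and 4, then 6, 8 and 10. With 6-week cycles these are weeks 6, 12, 18, 30, 42 and 54.
- SPD paths: assumed. The documents contain no SPD data.

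**Step 1: thresholds.** Set baseline SPD to 100 and let x be the fractional shrinkage, so nadir = 100(1 - x). The nadir rule triggers at 125(1 - x) and the baseline rule at 125. The regrowth from nadir needed under the baseline rule is 1.25/(1 - x) - 1; under the nadir rule it is always 25%.

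| Shrinkage | Nadir SPD | irPD, nadir rule | irPD, baseline rule | Regrowth needed, baseline rule |
|---|---|---|---|---|
| 0% | 100 | 125 | 125 | 25% |
| 30% | 70 | 87.5 | 125 | 79% |
| 50% | 50 | 62.5 | 125 | 150% |
| 70% | 30 | 37.5 | 125 | 317% |

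**Step 2: hypothetical patients.** irPD is the first scan with SPD at least 1.25 times the reference, which is either the running minimum including baseline, or baseline itself.

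| Path | SPD at successive scans | irPD week, nadir | irPD week, baseline | Clinical benefit, nadir / baseline |
|---|---|---|---|---|
| A | 70, 80, 90, 110, 130 | 18 (90 ≥ 87.5) | 42 (130 ≥ 125) | no / yes |
| B | 45, 40, 52, 90, 130 | 18 (52 ≥ 50) | 42 | yes / yes (confirmed irPR) |
| C | 70, 70, 75, 90, 110, 130 | 30 (90 ≥ 87.5) | 54 | yes / yes |
| D | 80, 130 | 12 | 12 | no / no |
| E | 70, 60, 60, 65, 70, 70 | none | none | yes / yes |
| F | 105, 115, 128 | 18 | 18 | no / no |

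The irRC PFS date moves by 24 weeks in A, B and C. Clinical benefit changes only in A, and response in none. The rules agree where both thresholds are crossed at the same scan (D), where regrowth never reaches 25% from nadir (E), and where there was no shrinkage (F). They also agree if the patient dies or is censored first.

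**Step 3: does the table settle it?** Take path B at week 18. SPD is 52 against a nadir of 40, so the change from nadir is 52/40 - 1 = +30% and target-lesion status is progressive under 11.3.1.2. The change from baseline is -48%. The table's progressive-disease row requires at least +25%. Read from baseline, no row fits this patient; read from nadir, the table contradicts 11.3.1.4. The column cannot be read wholly from nadir either, because the -50% cut is by definition from baseline.

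**Step 4: relation to RECIST.** If both diameters grow in proportion, a 25% rise in SPD is a rise of √1.25 - 1 = 11.8% in diameter. RECIST progression in 11.1.3.1 needs 20% and 5 mm. Under the nadir rule, irPD without new lesions could therefore come before RECIST progression.

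**The case against.** The best counter-argument is that 11.3.1.4 governs. The two preceding sections are headed as target and non-target response, whereas 11.3.1.4 concerns overall response and announces its own criteria, and PFS turns on overall response. A programmer could reasonably apply it. But the table that summarizes 11.3.1.4 takes the nadir-based target status as an input, Step 3 shows that the combination breaks down, and no text states a precedence.

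Other points have some force:

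- Objectives 1.3.5 and 1.3.6 also cite the published immune-related criteria, so Section 11.3 is not the only stated basis. That source was not available for this review. A citation does not remove a contradiction within the protocol's own text.
- The stakes are limited. This is a 30-patient single-arm study, the affected endpoints are secondary, and 13.4 plans no hypothesis tests for time-to-event endpoints.
- The six paths were chosen by hand, so the share that differ says nothing about frequency.
- The opening of Section 11 implies a scan near week 24 that footnote j omits. With steady regrowth, A and B would not change. In C the nadir-rule date could move to week 24; the baseline-rule date stays at week 54.
- Section 5.5 lists RECIST progression as the reason to stop and uses irRC only to permit continuation. That largely answers what happens if irPD comes first. It leaves unclear when the permission ends.
- The documents do not force the choice of nadir. Counting from baseline throughout would also give one date per patient. A single sentence giving 11.3.1.4 precedence would not suffice, because the table's target-status input would still be nadir-based.

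**Conclusion.** The concern holds. Section 11.3 contains two incompatible references for irPD, and neither the summary table nor Section 13.4 chooses between them. In the examples the irRC PFS date shifts by 24 weeks, and in one of them irRC clinical benefit reverses.

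The thresholds in Step 1 follow directly from the text. The sizes of the date shifts rest on assumed SPD paths and the footnote j scan weeks. The effect is confined to patients who shrink, regrow and cross the two thresholds at different scans, and the documents give no basis for estimating how many will. This should be corrected, but it does not threaten the primary analysis or the two-stage decision rule.

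**What to change.** Settle one irPD reference before any irRC endpoint is derived, so that the choice is not made with results in view.

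1. In 11.3.1.4, change both irPD criteria to a 25% increase over nadir SPD, defined as the smallest SPD on study, including baseline. This is the smallest consistent edit. It matches 11.3.1.2, 11.3.1.3 and the RECIST rule in 11.1.3.1, which counts progression "taking as reference the smallest sum on study (this includes the baseline sum if that is the smallest on study").
2. In the table, split or annotate the percent-change column: -50% from baseline for irPR, +25% from nadir for irPD. Do not relabel the whole column.
3. In 5.5, cross-refer to this irPD definition as the end of the allowance, and state which criterion applies if irPD comes before RECIST progression.

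The cost is two bullets, one table column and a cross-reference, with no new data. The drawback is that irPD will be called earlier than under the baseline wording in patients who shrink and regrow. Their irRC PFS may be somewhat shorter, and so may the time allowed on therapy to rule out pseudoprogression. If the sponsor prefers baseline for that reason, 11.3.1.2, 11.3.1.3 and the table must change instead.
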